4.2 Study Participants

Participant disposition, demographics and baseline characteristics will be summarized by tumor type, dose level and overall for FAS population.

Baseline will be defined as the last no missing observation prior to administration of IP, unless otherwise specified.

4.2.1 Participant Disposition

The number and percentage of participants who completed and discontinued screening period and reasons for discontinuation will be presented for all participants who signed the ICF.

A similar table for treatment and follow-up disposition will also be presented for the FAS by dose level and overall.

All disposition details and dates of first and last evaluations for each participant will be listed.

Number and percentage of participants for each analysis set will be summarized by dose level and overall.

4.2.2 Protocol Deviations

The number and percentage of participants with the following important protocol deviation criteria will be summarized for each criterion and overall, by dose level and overall, and

ISN/Protocol 5354-CL-1201

tumor type. Participants deviating from a criterion more than once will be counted once for the corresponding criterion.

The unique identifiers will be as follows:

PD 1: Inclusion/Exclusion

PD 2: Withdrawal Criteria

PD 3: Study Intervention

PD 4: Excluded Concomitant Medications

PD 5: Informed Consent

PD 6: Safety Reporting

PD 7: Procedures/Tests

4.2.3 Demographic and Other Baseline Characteristics

Demographic, and other baseline characteristics will be summarized descriptively by tumor type, dose level, and overall for the FAS.

Descriptive statistics for age, age categories (<65, >=65 - <75, >=75), body mass index (BMI), weight and height will be presented. Frequency tabulations for sex, ethnicity and race will be presented.

Medical history is coded in MedDRA, and will be summarized by System Organ Class (SOC) and Preferred Term (PT), by tumor type, dose level, and overall for the FAS.

Primary diagnosis of the target disease will be listed including T categorization in TNM classification by tumor type and dose level. For breast cancer laterality (left/right) will be presented by dose level. The location of tumor (extremities: upper/lower, left/right), trunk (front, back or side [L or R]), head, neck, other, tumor thickness, and ulceration status will be presented by melanoma and dose level.

4.2.4 Previous and Concomitant Medications

Previous and concomitant medications will be summarized by therapeutic subgroup (ATC 2nd level), chemical subgroup (ATC 4th level) and preferred WHO name (active ingredients for combination drugs) by tumor type and dose level for the SAF.

Participants taking the same medication multiple times will be counted once per medication and investigational period. A medication which can be classified into several chemical and/or therapeutic subgroups is presented in all chemical and therapeutic subgroups.

Previous medications are defined as medications that participants started prior to IP administration period. Concomitant medications are defined as any medications that participants took after IP administration until the end of follow up period. Medications that started prior to and continued after IP administration will be counted in both previous and concomitant medications.

ISN/Protocol 5354-CL-1201

4.2.5 Non-medication therapies

Frequency tabulations of subjects with non-medication therapy and reason for use will be presented by tumor type and dose level and overall for SAF.

4.2.6 Prior history imaging medication treatment

Frequency tabulations of subjects with prior history imaging medication treatment will be presented by tumor type and dose level and overall for SAF.

4.2.7 Extent of Exposure

Since this is a single dose study, the analysis of duration of exposure is not applicable. Study drug dosing information which include dosing date and time, volume prepared and administered from syringe, total drug used (derived following the pharmacy manual), compliance, number of injection sites, route of administration, directionality of the anatomical location, and location of administration will be listed.

4.2.8 SoC Visualization Agent used during biopsy

SoC visualization agent used during biopsy at Day 1 intraoperative will be summarized.

4.3 Primary Endpoint Analysis

The primary analysis will be conducted on the FAS. No statistical testing will be performed.

4.3.1 Definition of Endpoints

Optimal dose determination will be assessed based on the totality of collected data by the VRC based on:

- LN tissue visualized (Yes/No)
- Visualized tissue is lymphatic in origin based on pathologic confirmation
- The Likert Scale determination of the intensity of fluorescence (0 to 3)
- Proportion of identified LN with histopathologic confirmation of LN tissue by ASP5354 compared with SoC treatment with either Tc-99mSC or Lymphoseek

The optimal dose is defined as the dose that provides a better visualization compared with lower doses and a comparable visualization to the next higher dose. In the case where 2 doses performed equally, the lower dose would be selected. Cumulative visualization data from all treated participants will be used for optimal dose determination.

4.3.2 Main Analytical Approach

The optimal dose will be determined by VRC based on the totality of the data and including the following assessments: LN tissue visualized (Y/N), visualized tissue is lymphatic in origin based on pathologic confirmation, the Likert scale determination of the intensity of fluorescence, and proportion of identified LN with histopathologic confirmation of LN tissue by ASP5354 compared with SoC treatment with either Tc-99mSC or Lymphoseek. The individual listings for the visualization parameters not limited to the parameters above are created.

ISN/Protocol 5354-CL-1201

4.4 Secondary Endpoints Analysis

The secondary analysis will be conducted on the FAS. No statistical testing will be performed.

4.4.1 Definition of Endpoints

4.4.1.1 Lymph Node Level

- The number of LN identified intraoperatively.
- The number and percentage ^{a)} of LN identified intraoperatively by histopathologic confirmation.
- The number of sentinel LN identified intraoperatively.
- The number and percentage ^{b)} of sentinel LN identified intraoperatively by histopathologic confirmation.
 - a) The denominator is the number of LN identified intraoperatively.
 - b) The denominator is the number of sentinel LN identified intraoperatively.

Sentinel LN detailed:

- The number of sentinel LN identified by ASP5354 or SoC treatment with either Tc-99mSC or Lymphoseek.
- The number of sentinel LN identified by ASP5354 and SoC treatment with either Tc-99mSC or Lymphoseek.
- The number and percentage ^{c)} of sentinel LN identified by ASP5354 or SoC treatment with either Tc-99mSC or Lymphoseek with histopathologic confirmation.
- The number of sentinel LN identified by ASP5354.
- The number and percentage ^{c)} of sentinel LN identified by ASP5354 with histopathologic confirmation and 95% CI.
- The number of sentinel LN identified by SoC treatment with either Tc-99mSC or Lymphoseek.
- The number and percentage ^{c)} of sentinel LN identified by SoC treatment with either Tc-99mSC or Lymphoseek with histopathologic confirmation and 95% CI.
- The difference in proportion of identified sentinel LN with histopathologic confirmation of LN tissue between ASP5354 and SoC treatment with either Tc-99mSC or Lymphoseek and 95% CI.
 - c) The denominator is the number of sentinel LN identified intraoperatively by histopathologic confirmation.

ISN/Protocol 5354-CL-1201

LN detailed:

- The number of LN identified by ASP5354 or SoC treatment with either Tc-99mSC or Lymphoseek.

- The number of LN identified by ASP5354 and SoC treatment with either Tc-99mSC or Lymphoseek.
- The number and percentage ^{d)} of LN identified by ASP5354 or SoC treatment with either Tc-99mSC or Lymphoseek with histopathologic confirmation.
- The number of LN identified by ASP5354.
- The number and percentage ^{d)} of LN identified by ASP5354 with histopathologic confirmation* and 95% CI.
- The number of LN identified by SoC treatment with either Tc-99mSC or Lymphoseek.
- The number and percentage ^{d)} of LN identified by SoC treatment with either Tc-99mSC or Lymphoseek with histopathologic confirmation* and 95% CI.
- The difference in proportion of identified LN with histopathologic confirmation of LN tissue between ASP5354 and SoC treatment with either Tc-99mSC or Lymphoseek and 95% CI.
 - d) The denominator is the number of LN identified intraoperatively by histopathologic confirmation

4.4.1.2 Patient Level

- The number of LN identified intraoperatively per patient.
- The number of LN identified by histopathologic confirmation per patient.
- The number of LN identified by ASP5354 with histopathologic confirmation per patient.
- The number of LN identified by SoC treatment with either Tc-99mSC or Lymphoseek with histopathologic confirmation per patient.
- The number of LN identified by ASP5354 or SoC treatment with either Tc-99mSC or Lymphoseek with histopathologic confirmation per patient.
- The number of LN identified by ASP5354 and SoC treatment with either Tc-99mSC or Lymphoseek with histopathologic confirmation per patient.
- Proportion of participants with at least 1 LN detected with histopathologic confirmation of LN tissue using ASP5354 and 95% CI.
- Proportion of participants with at least 1 LN detected with histopathologic confirmation of LN tissue using SoC treatment with either Tc-99mSC or Lymphoseek and 95% CI.

ISN/Protocol 5354-CL-1201

 The difference in proportion of identified LN with histopathologic confirmation of LN tissue between ASP5354 and SoC treatment with either Tc-99mSC or Lymphoseek and 95% CI.

 Proportion of participants with at least 1 LN with histopathologic confirmation detected by the method other than ASP5354 or SoC treatment with either Tc-99mSC or Lymphoseek and 95% CI.

4.4.2 Main Analytical Approach

4.4.2.1 Lymph Node Level

The number of and percentage for lymph nodes or sentinel lymph nodes will be summarized per the specified denominator.

4.4.2.2 Patient Level

The number of and percentage for the detection of lymph nodes or sentinel lymph nodes per patient will be summarized with specified statistics.

4.5 Exploratory Endpoints Analysis

4.5.1 Patient Level

- The Maximum of Likert Scale of the intensity of the fluorescence in ASP5354 will be summarized by frequency and percentage.
- The average score of Likert Scale (0- None, 1- Mild, 2- Moderate, 3- Strong) in sentinel lymph nodes per patients for the intensity of the fluorescence in ASP5354 will be summarized by descriptive statistics.
- The Signal Background Ratio (SBR) in ASP5354 will be summarized using descriptive statistics.

The SBR will be defined as follows:

$$SBR = \frac{Mean\ region\ of\ interest}{Mean\ signal\ background}$$

based on Hoogstins et al, 2019. For SBR records where images are reviewed and no visualization occurs, the SBR will be imputed as 1 for the summary tables.

- The transdermal visualization of lymphatic spread of ASP5354 after injection will be summarized by frequency and percentage.
- The time from injection to surgical identification of LN(s) will be summarized by descriptive statistics.

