Participants will receive Tc-99mSC or Lymphoseek as part of SoC for SLN biopsy. In case the participant needs other surgery (e.g., lumpectomy, mastectomy etc.) on the same day of study drug administration, the other surgery is allowed once the SLN biopsy has completed. In the operating room, participants will receive ASP5354. After administration of ASP5354, visualization of the LN(s) will be assessed using a NIR-F imaging system followed by confirmation with the gamma probe. Once lymphatic mapping is completed, gamma probe will be used per SoC. For all the LNs observed by ASP5354, gamma probe will be attempted to measure radioactivity. If the LN is not observed with NIR-F after approximately 15 minutes following injection for breast cancer participants and approximately 15 to 30 minutes for melanoma participants depending on the location of the tumor and LNs, the investigator can proceed to use the gamma probe for LN detection. When the LN is detected with the gamma probe first, radioactivity will be measured and then NIR-F imaging should be attempted again for LN visualization. For participants with melanoma, usage of lymphoscintigraphy or SPECT as part of SoC is also allowed.

The visualization data to be collected will consist of the following:

- The visualization of the LN(s) will be assessed by the investigator intraoperatively using a binary “Yes or No” question.
 - If “Yes,” the time of surgical identification of LN(s) will be collected by the investigator.
 - If “Yes,” the number of LNs visualized and the number of LNs visualized with histopathology confirmed LN will be also assessed by the investigator.
Note: Histopathology review will be conducted per standard practice at each site.
- Transdermal visualization of lymphatic spread of ASP5354 after injection of the drug will also be assessed using a binary “Yes or No” question.
- The fluorescence intensity of the LN will be qualitatively assessed using a Likert Scale (0 = None; 1 = Mild; 2 = Moderate; and 3 = Strong).
- The radioactivity count will be collected for all the LNs identified by ASP5354 and/or SoC.
- The number of LN(s) with metastatic spread will be assessed based on histopathologic review.
Note: Histopathology review will be conducted per standard practice at each site.

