7.1.1 Primary and Secondary Efficacy Assessments

Either during or post-operatively, the investigator will evaluate the details of all the LNs identified either by ASP5354 or Gamma Probe. These data will be captured to eCRF.

Following data is captured in eCRF per participant.

- Identification of at least 1 LN detected by ASP5354 and/or Tc-99mSC or Lymphoseek
- Times of injection of ASP5354 and Tc-99mSC or Lymphoseek
- Location (i.e., 3 and 9 o'clock) of ASP5354 administration
- Time of start of surgery
- Time of surgical identification of the LN(s) by ASP5354
- Time of incision for lymphatic mapping
- Time of removal of first LN
- Time of end of surgery
- Transdermal visualization of lymphatic spread of ASP5354 after injection

Following data is captured in eCRF per LN.

- “Sentinel LN” or “Non-sentinel LN”
- Method of identification (ASP5354 and/or Tc-99mSC or Lymphoseek)
- Dissection of LN tissue identified*
- Histopathologic confirmation of LN tissue by pathologist*

- Histopathologic confirmation of metastatic spread by pathologist*
- Likert scale:
The intensity of fluorescence will be qualitatively assessed during surgery by the investigator, by direct examination of the LN. Likert Scale (0 = None, 1 = Mild, 2 = Moderate and 3 = Strong) will be used to determine the intensity of fluorescence at the time point of the LN identification.
- Radioactivity count:
The radioactivity count of all the LNs identified by ASP5354 and /or Tc-99mSC or Lymphoseek will be counted with gamma probe.
* may not be collected in case of Non-Sentinel LN

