9.3.4 Exploratory Endpoint(s)/Estimand(s) Analysis

The Likert Scale of the intensity of the fluorescence will be summarized by frequency and percentage by dose group.

The SBR will be summarized using descriptive statistics by dose group.

The transdermal visualization of lymphatic spread of ASP5354 after injection will be summarized by frequency and percentage by dose group.

The time from injection to surgical identification of LN(s) will be summarized by descriptive statistics by dose group.

The frequency and percentage of participants with visualization of LNs using ASP5354 will be summarized by dose group. In addition, the number of LNs visualized using ASP5354 will be summarized by descriptive statistics by dose group.

The exploratory analysis will be performed using the FAS.

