4.6 Other Endpoints

4.6.1 Green Coloration of Urine or Skin

The frequency and percentage of patients who experience green coloration of urine will be summarized by dose level and tumor type only for subjects who used urethral catheter. The duration of green coloration of urine or skin (in hours) will be summarized using descriptive statistics by dose level and tumor type. The duration is calculated from first date/time point of green coloration of urine or skin to last date/time point of green skin coloration. If the green coloration of urine or skin is still present at discharge, the duration is from first date/time point of green coloration to the date/time of discharge.

Additional to descriptive statistics, if applicable, the duration will be analyzed using Kaplan Meier estimation. For this purpose, subjects with green coloration of urine or skin at discharge are censored at the time point of discharge.

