4.11 Additional Conventions

4.11.1 Missing Data

As a general principle, no imputation of missing data will be done. Exceptions are the start and stop dates of AEs and concomitant medications if they are missing

In case of missing or partial start and stop dates for concomitant medications, the following rules will be used:

If the start date is missing or partial:

- if the month is missing, use January
- if the day is missing, use the first day of the month under consideration
- if the year is missing, use year of the informed consent date
- if the entire date is missing, use informed consent date

If the stop date is missing or partial:

- if the month is missing, use December
- if the day is missing, use the last day of the month under consideration
- if the year or the entire date is missing, set the stop date to December 31st, 2099

If the imputed start date is after the stop date, then the imputed start date will be 1 day prior to the stop date.

For AEs, a missing or incomplete onset date will be imputed according to the following conventions.

ISN/Protocol 5354-CL-1201

If only the year is known for the AE onset date, the imputed onset date will be the latest of the following non-missing dates:

- Date of first dose of study drug
- January 1 of the year of AE onset date

If only the month and year is known for the onset date, set the surrogate onset date to the first day of that month and then apply the following rules.

- If the month and year of the onset date is prior to the month and year of the first dose of study drug, then the surrogate onset date will be the imputed onset date.
- If the month and year of the onset date is on or after the month and year of the first dose of study drug, then the imputed onset date will be the latest of the following non-missing dates:
 - Date of first dose of study drug
 - Surrogate onset date

If the imputed onset date is after the adverse event end date, the imputed onset date will be the same as the adverse event end date.

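### Time from injection to lymph node identification is summarized only where ASP5354 showed a node, so its mean and median cannot be compared across doses with different failure rates

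*SAP*

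**What the plan says.** The SAP's analysis of this endpoint is one line in section 4.5.1: "The time from injection to surgical identification of LN(s) will be summarized by descriptive statistics". Protocol 9.3.4 matches it ("The time from injection to surgical identification of LN(s) will be summarized by descriptive statistics by dose group") and places the exploratory analyses on the Full Analysis Set (FAS).

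Three other provisions decide who contributes a value:

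- **Collection.** In Protocol 4.1 the visualization question is yes or no, and only after a yes does the plan say "the time of surgical identification of LN(s) will be collected by the investigator".
- **Agent.** The case report form item in Protocol 7.1.1 is "Time of surgical identification of the LN(s) by ASP5354". A node found only by gamma probe supplies no time.
- **Missing data.** SAP 4.11.1: "As a general principle, no imputation of missing data will be done". The exceptions are adverse event and concomitant medication dates.

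The procedure matters too. If near-infrared imaging shows no node after about 15 minutes (breast cancer) or 15 to 30 minutes (melanoma), the surgeon can go to the gamma probe. Protocol 4.1 continues: "When the LN is detected with the gamma probe first, radioactivity will be measured and then NIR-F imaging should be attempted again".

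Elsewhere the SAP does provide for similar cases. For the signal background ratio, in the same section: "For SBR records where images are reviewed and no visualization occurs, the SBR will be imputed as 1 for the summary tables". For the duration of green coloration, SAP 4.6.1 plans Kaplan-Meier estimation in which "subjects with green coloration of urine or skin at discharge are censored at the time point of discharge".

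**The concern.** No provision gives a censoring time, rank or value to a participant in whom ASP5354 showed no node. The analysis set is nominally the FAS, but failures cannot enter the mean or median. That loss depends on dose, because failing to show a node is one of the things expected to differ between doses.

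A by-dose table of times then invites a comparison it cannot support. One dose's median may rest on nearly everyone treated and another's on the minority who lit up. Late times may also partly reflect when the gamma probe was used and the second look taken, rather than how fast the agent travelled. The review committee works from the totality of the data and its criteria are expressly not exhaustive, so such a table could reach its discussion of dose.

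**Working it through.** **Inputs from the documents.** The plan gives no identification times or success rates, so it has no figure for this endpoint to reproduce. It gives up to 12 participants per dose level (3 × 12 = 36 per tumor type for the initial levels) and the 15-minute and 15-to-30-minute marks for turning to the gamma probe.

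**Assumptions.** Time T to a node being visible is lognormal with median m and log-SD s = 0.5. The two doses compared have true medians of 8 and 20 minutes, a true gap of 12 minutes.

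**Case A: nothing is identified after 15 minutes.** Success is p = Φ(ln(15/m)/s). The median among successes is m·exp(s·Φ⁻¹(p/2)).

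- m = 8: p = Φ(1.257) = 0.896; median 8·exp(0.5 × −0.131) = 7.5 min.
- m = 15: p = Φ(0) = 0.50; median 15·exp(0.5 × −0.674) = 10.7 min.
- m = 20: p = Φ(−0.575) = 0.283; median 20·exp(0.5 × −1.075) = 11.7 min.

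The 12-minute gap shows as 11.7 − 7.5 = 4.2 minutes. With log-SD from 0.3 to 0.8 it shows as 5.3 to 3.2 minutes. With a 30-minute cut-off and log-SD 0.5 it shows as 17.5 − 8.0 = 9.5 minutes.

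**Case B: one second look at time R.** Any node that became visible between 15 minutes and R is recorded at R. R is an assumption, since the documents give none. The recorded median is the point where half of P(T ≤ R) has accrued: m·exp(s·Φ⁻¹(P(T ≤ R)/2)) if that falls by 15 minutes, otherwise R.

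| R (min) | P(T ≤ R), m = 8 | P(T ≤ R), m = 20 | Recorded medians (min) | Recorded gap (min) |
|---|---|---|---|---|
| 20 | 0.967 | 0.500 | 7.8 and 14.3 | 6.4 |
| 25 | 0.989 | 0.672 | 7.9 and 25.0 | 17.1 |
| 30 | 0.996 | 0.791 | 8.0 and 30.0 | 22.0 |

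For m = 20, 0.283 of participants are identified by 15 minutes. At R = 25, half of 0.672 is 0.336, which exceeds 0.283, so the median falls on the second look itself. The same happens at R = 30.

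**Case C: failures never light up.** If successes at every dose share one time distribution, the expected difference among successes is zero whatever the failure rates.

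**Illustration at 12 per dose (invented times).** Dose 1 identifies 11 of 12, at 4, 4, 5, 5, 6, 6, 7, 7, 8, 9 and 10 minutes. Dose 2 identifies 4 of 12, at 5, 6, 7 and 8 minutes. Among successes the medians are 6.0 and 6.5 minutes. Over all 12, with failures ranked last, they are (6 + 7)/2 = 6.5 minutes and not reached.

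**The case against.** The strongest reply is that a weak dose cannot hide. Descriptive statistics in SAP 4.1 include n, so a median resting on 4 of 12 is visible as such. Protocol 9.3.4 reports the percentage visualized by dose, and Protocol 9.3.3 and SAP 4.4.1.2 report the proportion with a confirmed node, with a 95% interval. Time is exploratory, is not among the listed committee criteria, and no hypothesis is tested. All of this stands and limits the impact. It does not make the medians comparable: n shows how many participants are missing without correcting for them.

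Two stronger readings are tempting and are not supported.

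- **That the bias always runs toward no difference.** This would follow if times stopped at 15 minutes. They do not: that mark is when the gamma probe may come in, and near-infrared imaging is to be tried again afterwards. Case B shows that the recorded gap can exceed the true one. Even in Case A, 11.7 against 7.5 minutes is visibly slower.
- **That the summary undermines the claim of shorter transit.** The claim in Protocol 2.1 and 2.2 compares ASP5354 with indocyanine green in nonclinical studies. This trial has no indocyanine green arm, so no by-dose time summary can test it.

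**Conclusion.** The concern holds in a limited form. As planned, the mean and median time are conditional on ASP5354 having shown a node and are not comparable across doses with different failure rates. The documents do not say successes only in so many words. It follows from conditional collection, the ASP5354-specific field and the rule against imputation.

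Neither size nor direction can be fixed from the documents. Under the stated lognormal assumptions a true 12-minute gap could appear as about 4 minutes, or as about 6 to 22 minutes with a second look at 20 to 30 minutes. Under a never-light-up assumption a difference can disappear. This is a worthwhile, inexpensive improvement to an exploratory analysis and does not threaten the primary objective.

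**What to change.** In SAP 4.5.1, by tumor type and dose level:

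1. Report for all FAS participants the cumulative proportion with a first lymph node identified by near-infrared imaging by 10, 15 and 30 minutes and by the end of the procedure. Keep never-identified participants in the denominator. Take the median from that curve, stated as not reached where it applies.
2. Label any summary restricted to successes as conditional, and print n/N beside it.
3. Show identifications made after gamma-probe detection separately only where the order can be recovered from the recorded data or video. Protocol 7.1.1 lists the method of identification but no item for its order, so this part should be optional.

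Items 1 and 2 use injection and identification times and the yes/no answer, all already collected. The cost is SAP wording and one extra table or figure. The estimates will be imprecise: at 6 of 12, the exact 95% interval (Beta quantiles, 0.025 of Beta(6, 7) and 0.975 of Beta(7, 6)) runs from 21% to 79%. No surgical step changes.
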